10.4. Withdrawal From the Study

A subject will be withdrawn from the study for any of the following reasons:

- Lost to follow-up
- Withdrawal of consent
- Death
- The subject's parent(s)/caregiver(s) is poorly compliant with study procedures, visits, and assessments, preferably after evaluation and discussion between the investigator and the sponsor
- Decision by the sponsor to stop or cancel the study
- Decision by the investigator to withdraw the subject from the study

If a subject is lost to follow-up, every reasonable effort must be made by the study-site personnel to contact the subject parent(s)/caregiver(s) and determine the reason for discontinuation/withdrawal. The measures taken to follow-up must be documented.

In case subjects prematurely discontinue study drug treatment for any reason (except withdrawal of consent), the parent(s)/caregiver(s) will be asked to continue with the subject's remaining study visits and assessment schedule, or, at a minimum, to return with the subject to the site for a Withdrawal and a Safety Follow-up Visit. At the Withdrawal and Safety Follow-up Visits, the same assessments as on the Day 8 and Day 21 visits, respectively, will be performed. In case the subject's legally acceptable representative(s) withdraw consent during the treatment or follow-up phase, an optional Withdrawal and Safety Follow-up Visit will be offered. At these optional Withdrawal and Safety Follow-up Visits, the same assessments as on the Day 8 and Day 21 visits, respectively, will be performed.

When a subject's parent(s)/caregiver(s) withdraw(s) the subject before completing the study, the reason for withdrawal is to be documented in the eCRF and in the source document. Study drug assigned to the withdrawn subject may not be assigned to another subject. If a subject is withdrawn from the study before the end of the double-blind treatment period, every attempt should be made to obtain follow-up assessments (see [TIME AND EVENTS SCHEDULE](#)).

10.5. Withdrawal From the Use of Samples in Future Research

The subject may withdraw consent for use of samples for research (refer to Section [16.2.5](#), Long-Term Retention of Samples for Additional Future Research). In such a case, samples will be destroyed after they are no longer needed for the clinical study. Details of the sample retention for research are presented in the main ICF.

11. STATISTICAL METHODS

Statistical analysis will be done by the sponsor or under the authority of the sponsor. A general description of the statistical methods to be used to analyze the efficacy and safety data is outlined below. Specific details will be provided in the Statistical Analysis Plan.

Analyses will be performed on the combined dataset of hospital and outpatient subjects, as well as on data of each cohort separately.

11.1. Interim Analyses

Up to 4 interim analyses are planned (see [Figure 2](#)). During and after all interim analyses, investigators, subject(s), and local sponsor representatives (except for selected local sponsor representatives from Japan) will remain blinded. An IDMC will monitor and review data in an unblinded manner, at all interim analyses. Enrollment will continue during each of the interim analyses.

During the first interim analysis, the Sponsor Committee will be unblinded; the central sponsor team members and local sponsor representatives from Japan will remain blinded. For the second interim analysis, the Sponsor Committee, central sponsor team members, and selected local

sponsor representatives from Japan will be unblinded upon recommendation from the IDMC and the Sponsor Committee. During any interim analysis taking place after the second interim analysis, the sponsor, including the central study team, and selected local sponsor representatives from Japan will be unblinded. Aggregate unblinded data and certain individual safety events may be shared with investigators to support the revised risk-benefit evaluation for the current study and to support start of Phase 3.

A Sponsor Committee, consisting of senior sponsor personnel not involved in the conduct of the study, will be established and will be responsible for decision making, considering the IDMC recommendation, and will communicate these decisions to the study team. Details are provided in the IDMC Charter.

The central sponsor team includes the following functions: clinical leader, statistician, virologist, PK leader, pharmacometrist, medical writers, and statistical programmers.

Additional interim analyses may be performed at the sponsor's discretion to support decision making for further development of JNJ-53718678 and to support interactions with health authorities.

Further details regarding the interim analyses will be specified in the SAP. Operating characteristics (power, Type I error, ...) of statistical decision procedures and methods at the interim analyses will be evaluated through computer simulations and summarized in a modeling & simulation report.

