9.3.1 Specific Toxicities and Safety Topics of Special Interest	
10.3 Discontinuation of Study Treatment	
ATTACHMENTS	

Rationale: A table presenting the risk factors for severe RSV disease was added to avoid stratification errors.
	

Applicable Section(s)	Description of Change(s)
3.1 Overview of Study Design	
Rationale: The statement on additional interim analyses (already included in the protocol body) was added to the synopsis and Section 3.1 for completeness.

SYNOPSIS	
3.1 Overview of Study Design	
Rationale: A statement was added on sharing selected unblinded data with investigators to support the revised risk-benefit evaluation for the current study and to support start of Phase 3.

SYNOPSIS	
11.1 Interim Analyses	
Rationale: A clarification was added (ULN are adult ULN) to the creatinine values of subjects older than 3 months of age in Attachment 1 (DMID Pediatric Toxicity Tables) based on feedback from the DMID Authors.

Attachment 1: Division of Microbiology and Infectious Diseases (DMID) Pediatric Toxicity Tables (November 2007; draft)	
Rationale:	The medication log was updated given the change in dose regimen from qd to bid. In order to make efficient updates to the ePRO system, the initial study medication log with slight modification will be repeated to allow capturing of dose intake information bid.

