During and after all interim analyses, investigators, subject(s), and local sponsor representatives (except for selected local sponsor representatives from Japan) will remain blinded. An IDMC will monitor and review data in an unblinded manner, at all interim analyses. During the first interim analysis, the Sponsor Committee will be unblinded; the central sponsor team members and local sponsor representatives from Japan will remain blinded. For the second interim analysis, the Sponsor Committee, central sponsor team members, and selected local sponsor representatives from Japan will be unblinded upon recommendation from the IDMC and the Sponsor Committee. During any interim analysis taking place after the second interim analysis, the sponsor, including the central study team, and selected local sponsor representatives from Japan will be unblinded. Aggregate unblinded data and certain individual safety events may be shared with investigators to support the revised risk-benefit evaluation for the current study and to support start of Phase 3.

A separate substudy may be performed at selected study sites to explore the feasibility of the use of biosensors for the evaluation of cardio-respiratory parameters (eg, respiratory rate, heart rate, and SpO₂). Details, including objectives and study design, will be described in a separate substudy protocol.

SUBJECT POPULATION

Screening for eligible subjects will be performed as soon as possible after initial presentation at the hospital (Cohort 1) or after presentation for medical care as outpatients (Cohort 2) such that subjects are randomized within 5 days of symptom onset. Within each cohort, except for the subcohort, randomization will be stratified by time of symptom onset (≤ 3 days vs > 3 days to ≤ 5 days before randomization) and by presence of risk factors for severe RSV disease (otherwise healthy vs presence of [a] risk factor[s] for severe RSV disease as defined above).

Key Inclusion Criteria

- The subject is a boy or girl ≥ 28 days and ≤ 3 years at the time of consent.
- The subject has been diagnosed with RSV infection using a preferably rapid PCR- or other molecular-based diagnostic assay (preferred) or a rapid-antigen-detection assay.

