3.2. Study Design Rationale

This Phase 2 multicenter, double-blind, placebo-controlled, randomized study is designed to explore the antiviral activity, clinical outcomes, safety, tolerability, and PK/PD relationships of high and low doses of JNJ-53718678 twice daily for 7 days in children ≥28 days and ≤3 years of age with acute respiratory tract infection due to RSV, in 2 cohorts ie, hospitalized (Cohort 1) and outpatients (Cohort 2). The results of this study will enable selection of the dose and clinical endpoints for subsequent Phase 3 studies.

Blinding, Control, Study Phase/Periods, Intervention Groups

There is currently no approved treatment routinely used for the treatment of RSV infection. A placebo control will be used to establish the frequency and magnitude of changes in virologic and clinical endpoints that may occur in the absence of active treatment. The use of a placebo

control will allow for any AEs or laboratory abnormalities observed during the course of the study to be evaluated properly, ie, to differentiate between events potentially related to the use of JNJ-53718678 vs those related to the underlying disease.

Randomization will be used to minimize bias in the assignment of subjects to treatment groups, to increase the likelihood that known and unknown subject attributes (eg, demographic and baseline characteristics) are evenly balanced across treatment groups, and to enhance the validity of statistical comparisons across treatment groups. Blinded treatment will be used to reduce potential bias during data collection and evaluation of clinical endpoints.

Within each cohort (including the subcohort of Cohort 1), eligible subjects will be randomized 1:1:1 to receive either a low or a high dose of JNJ-53718678, or placebo (see Section 6). For dosing purposes, 3 age groups (≥ 28 days and < 3 months; ≥ 3 months and < 6 months or ≥ 6 months and ≤ 3 years of age) are defined depending on the subject's age at the time of consent, taking into account the abundance of specific enzymes (and their maturation) involved in the metabolism of JNJ-53718678 in these different age groups (see also Study 53718678RSV1005).

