The sponsor assumes responsibility for appropriate reporting of AEs to the regulatory authorities. The sponsor will also report to the investigator (and the head of the investigational institute where required) all suspected unexpected serious adverse reactions (SUSARs). For anticipated events reported as individual serious adverse events the sponsor will make a determination of relatedness in addition to and independent of the investigator's assessment. The sponsor will periodically evaluate the accumulating data and, when there is sufficient evidence and the sponsor has determined there is a reasonable possibility that the intervention caused a serious anticipated event, they will submit a safety report in narrative format to the investigators (and the head of the investigational institute where required). The sponsor assumes responsibility for appropriate reporting of anticipated events to the regulatory authorities according to requirements of the countries in which the studies are conducted. The investigator (or sponsor where required) must report SUSARs to the appropriate Independent Ethics Committee/Institutional Review Board (IEC/IRB) that approved the protocol unless otherwise required and documented by the IEC/IRB. A SUSAR will be reported to regulatory authorities unblinded. Participating investigators and IEC/IRB will receive a blinded SUSAR summary, unless otherwise specified.

For all studies with an outpatient phase, including open-label studies, the subject must be provided with a "wallet (study) card" and instructed to carry this card with them for the duration of the study indicating the following:

- Study number
- Statement, in the local language(s), that the subject is participating in a clinical study
- Investigator's name and 24-hour contact telephone number
- Local sponsor's name and 24-hour contact telephone number (for medical staff only)
- Site number
- Subject number
- Any other information that is required to do an emergency breaking of the blind

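### Investigators are said to remain blinded, yet unblinded aggregate interim results, not limited to safety, may be shared with them while they still enrol and rate Cohort 2 children

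*Protocol*

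**What the plan says.** Section 11.1 states the rule: "During and after all interim analyses, investigators, subject(s), and local sponsor representatives (except for selected local sponsor representatives from Japan) will remain blinded". Its next paragraph adds the permission: "Aggregate unblinded data and certain individual safety events may be shared with investigators to support the revised risk-benefit evaluation for the current study", with support for starting Phase 3 as a second purpose. The Synopsis repeats both sentences, in its design overview and in its statistical methods. Neither place limits the permission by type of data, by date or by recipient.

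Other sections bear on it:

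- Section 11.1: "Enrollment will continue during each of the interim analyses".
- Section 3.2 gives the reason for masking: "Blinded treatment will be used to reduce potential bias during data collection and evaluation of clinical endpoints".
- Section 5 says that investigators are not given randomization codes.
- Section 12.3.1 sets the default for serious unexpected reactions: "Participating investigators and IEC/IRB will receive a blinded SUSAR summary, unless otherwise specified".
- Section 2.1.2 makes the clinician PRESORS, scored by the investigator, a source of secondary endpoints.

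**The concern.** Read together, the two sentences in Section 11.1 do not say what investigators are blinded to. If the word covers interim results, the permission contradicts it. If it covers only each child's allocation, the protocol never says so.

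The recipients are the people whose judgement is to be protected. Investigators assess the entry symptoms (Section 4.1), score the clinician PRESORS, decide whether a complication is associated with RSV, judge the relatedness of adverse events, and may stop a child's treatment. The Day 8 clinician PRESORS also determines which children are swabbed daily up to Day 13 (Section 9.2.1).

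Time to resolution and symptom severity are the candidates that Section 11.1.3 expects for selection at interim 3, and these rest partly on the clinician's score. The Phase 3 purpose does nothing for the children in this trial, so their safety cannot justify releasing efficacy results to the people rating them.

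**Working it through.** The protocol gives no figure on this point to reproduce. The check has three parts.

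**1. Children exposed.** Interim 3 is triggered when about 70 to 80 Cohort 2 children have completed Day 14 (Section 11.1.3). Cohort 2 is planned at 150, with a maximum of 300.

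- Planned size: 150 − 80 = 70 and 150 − 70 = 80 children, or 70/150 = 47% to 80/150 = 53%.
- Maximum size: 300 − 80 = 220 and 300 − 70 = 230 children, or 220/300 = 73% to 230/300 = 77%.

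These children have yet to complete Day 14. Because enrolment continues, some are already enrolled, so the counts are upper bounds.

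**2. What a site can infer about allocation.** The suspension is 20 mg/mL for both doses. The volume per intake is provided to the site (Section 6), the pharmacist, site staff or caregivers draw it up (Section 14.2), and the medication log that staff review daily records it (Section 7, Attachment 6). Volume per kg is dose divided by 20:

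| Age group | High stream | Low stream |
|---|---|---|
| 1 | 2.5/20 = 0.125 mL/kg | 0.85/20 = 0.0425 mL/kg |
| 2 | 3.0/20 = 0.150 mL/kg | 1.0/20 = 0.050 mL/kg |
| 3 | 4.5/20 = 0.225 mL/kg | 1.5/20 = 0.075 mL/kg |

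Within an age group the streams differ about threefold, so weight and volume identify the stream. Allocation is 2:2:1:1 (low dose, high dose, low-volume placebo, high-volume placebo; Section 5). A high-volume child is therefore on high dose with probability 2/(2+1) = 2/3 and on low dose with probability 0.

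**3. Size of a possible effect (illustration).** Suppose sites learn that the high dose looks better and then rate high-volume children better by b standard deviations. The documents give no value for b; 0.2 and 0.5 are assumed. The mean shift after release is b in the high-dose arm, b/2 in placebo (half of it is high-volume) and 0 in the low-dose arm. Let f be the share rated after release and n the number per arm. The one-sided error at nominal 2.5% is Φ(d/√(2/n) − 1.96), where d = f·b/2 for high dose versus placebo and d = f·b for high versus low dose.

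With n = 50 and f = (150 − 75)/150 = 0.5, √(2/50) = 0.2:

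- High versus placebo, b = 0.2: d = 0.05, Φ(0.25 − 1.96) = 4.4%.
- High versus placebo, b = 0.5: d = 0.125, Φ(0.625 − 1.96) = 9.1%.
- High versus low, b = 0.2: d = 0.10, Φ(0.5 − 1.96) = 7.2%.
- High versus low, b = 0.5: d = 0.25, Φ(1.25 − 1.96) = 23.9%.

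With n = 100 and f = (300 − 75)/300 = 0.75, √(2/100) = 0.141. High versus placebo becomes Φ(0.075/0.141 − 1.96) = 7.6% for b = 0.2 and Φ(0.1875/0.141 − 1.96) = 26.3% for b = 0.5.

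If raters could guess the arm no better than chance, d would be 0 and the error would stay at 2.5%.

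**The case against.** The best defence is that masking here means subject-level allocation. Codes are withheld and the placebo is volume-matched, and an aggregate result does not say which arm a given child is in. On that reading the two sentences can coexist, and a rater guessing at chance introduces no expected difference between arms. The first half is a possible reading, though the protocol never states it. The second half fails in this design, because volume and weight rule out one active arm for every child and make the other twice as likely as placebo.

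Several other points stand:

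- Sharing is optional, and the protocol shows no release of arm-level efficacy to sites. The interim findings that it reports for this study (Sections 1.1 and 1.2.5) concern safety and are not given by arm.
- The permission has a legitimate root. It came with the amendment prompted by the QT finding, and Section 16.1 requires that families receive new information relevant to their decision.
- A reader might infer that individual events will be released with their treatment. The operative text attaches the word unblinded only to the aggregate data. The amendment summary speaks of "A statement was added on sharing selected unblinded data with investigators", which leans towards that reading without settling it.
- A reader might see a conflict with the blinded SUSAR default. That sentence allows exceptions, so it shows the usual practice and contradicts nothing.
- A reader might infer that the exposed endpoints are already the confirmatory ones. None has been selected; Section 11.1.3 names only expected candidates.
- Central randomization means that a change in whom sites enrol would alter case mix, not the comparison between arms.

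**Conclusion.** The point holds as a defect of wording with a real but conditional risk. Section 11.1 and the Synopsis promise blinding and, without defining it, permit release of unblinded aggregate results of any kind to investigators who are still enrolling and rating. The documents do not support saying that the rated endpoints will be biased, or that the primary analysis is at risk, since viral load is measured by qRT-PCR in a central laboratory.

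What is exposed is the clinician PRESORS, the other investigator judgements and, through the Day 8 score, the later swab schedule. Up to 47-53% of Cohort 2 would still have to complete Day 14 if release followed interim 3, or up to 73-77% after expansion to 300. The error rates above rest on an assumed rating shift, on release of arm-level efficacy soon after interim 3, on raters knowing the volume given, and on a simple pairwise comparison of a continuous score. They show that a modest shift could matter, and they do not predict one.

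**What to change.** In Section 11.1 and both places in the Synopsis, replace the sharing sentence with text to this effect:

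- For investigators, blinded means blinded to subject-level allocation and to arm-level efficacy results.
- Until the last subject's Day 28 contact, investigators active in this trial may receive only the aggregate safety data needed for the risk-benefit evaluation of this study.
- Individual safety events are shared without treatment assignment, unless subject safety requires otherwise.
- Arm-level efficacy (viral load, PRESORS, time-to-event results) is withheld from these investigators until that date, including for Phase 3 preparation.

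It would also help to record the date and recipients of any release, so that ratings before and after it can be compared.

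The change is to wording only. The safety update to sites and families is kept. The downside is that investigators taking part in both this trial and Phase 3 see interim efficacy results later.

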11.1.1. First Interim Analysis

The first interim analysis encompassing safety and tolerability, PK, and antiviral effect is planned when at least 36 subjects from Cohort 1 have completed the Day 14 assessments (or discontinued earlier). Enrollment in Cohort 1 (including the subcohort) will continue during the interim analysis and IDMC review.

Enrollment in the >3 days to \leq 5 days since symptom onset stratum might be temporarily paused prior to interim analysis 1 (at N 36 in Cohort 1), once the maximum number of subjects are enrolled in the >3 days to \leq 5 days since symptom onset stratum in Cohort 1. Enrollment in the >3 days to \leq 5 days since symptom onset stratum will be reopened once the last subject required for interim analysis 1 has been randomized.

An IDMC will review the interim data, and will issue its recommendation to the sponsor, based on which the Sponsor Committee will decide whether to initiate enrollment in Cohort 2, while hospitalized subjects continue to be enrolled (see also Section 11.12).

11.1.2. Second Interim Analysis

A second interim analysis is planned, preferably at the end of a hemispheric RSV season, when approximately 70 to 80 subjects from Cohort 1 (regardless of the number of subjects in the subcohort having reached the target of 6) have completed the Day 14 assessments (or discontinued earlier). Enrollment in the >3 days to \leq 5 days since symptom onset stratum might be temporarily

paused prior to interim analysis 2 (at N approximately 70-80 in Cohort 1), once the maximum number of subjects are enrolled in the >3 days to ≤5 days since symptom onset stratum in Cohort 1. Enrollment in the >3 days to ≤5 days since symptom onset stratum will be reopened once the last subject required for interim analysis 2 has been randomized. During this interim analysis, a futility and population enrichment analysis will be performed on antiviral activity and one clinical endpoint (ie, time to resolution of symptoms, considering data of both cohorts). In addition, other clinical course and safety-related endpoints will be analyzed. An IDMC will review the interim data and will issue its recommendation to the sponsor, based on which the Sponsor Committee will decide whether to terminate the study for futility, or to terminate the enrollment of the >3 days since symptom onset population. The decision rules will be defined in the SAP.

Depending on enrollment status of Cohort 2, the second interim analysis will not be performed, if it is later than or too close to the predicted timing of the planned third interim analysis.

